8.2 Sample Size Considerations

Approximately 26 patients will be randomly assigned to each treatment sequence to ensure that at least 46 patients in total complete the 2 treatment periods. The primary comparison will be the estimate of the mean treatment difference between nabiximols and placebo in the mean change from baseline in LLMT-6.

Assuming a standard deviation of the paired differences between nabiximols and placebo of 0.71 and a treatment difference of -0.30, 46 patients will provide 80% power using a 5% significance level and a two-sided test. Adjusting for 10% dropout, a total of approximately N=52 patients are required. If more than 6 patients withdraw from the trial, additional patients will be enrolled to have 46 completers.

A blinded sample size re-estimation was conducted based on methodology in section 11.1 and the estimated standard deviation of the pooled treatment period differences (treatment period 2 – treatment period 1) in changes from baseline to D21 in MAS was larger than 0.71 (the assumed standard deviation of the treatment differences at design stage). Using this new standard deviation as the estimate of the standard deviation of the treatment differences (nabiximols – placebo) of the changes from baseline to D21 in MAS, the sample size was recalculated. In a blinded sample size re-estimation committee meeting dated 30th November 2021, the committee recommended increasing the sample size to 68 completers. This new sample size will result in at least 80% power for this study if the new observed blinded standard deviation were the true unblinded standard deviation, and greater than 90% power if the true unblinded standard deviation was exactly 0.71.

SAS software version 9.4 was used to perform the sample size calculations.

8.3 Randomization

At Visit 2, in the morning of Day 1, eligible patients will be randomly assigned in a 1:1 ratio to 1 of 2 treatment sequences, each composed of 2 treatment periods, with administration of multiple doses of nabiximols or placebo following the randomization schedule generated and kept by Endpoint.

Enrolled patients will be allocated a unique patient number in a sequential order by trial site. Following randomization, GW Pharma Limited will provide all IMP in a packed and labelled state, and the Interactive Web Response Technology (IRT) will identify the pack number to be dispensed to the patient at each relevant visit according to the treatment sequence assigned in the randomization schedule.

9.0 Study Endpoints, Variables and Covariates

9.1 Overview

An overview of objectives and endpoints is shown in [Table 9.1-1](#) and an overview of estimands is shown in [Table 9.1-2](#).

Table 9.1-1 Objectives and Endpoints

Objectives and Endpoints	
Primary Objective	Primary Endpoint

 To evaluate the effect of multiple doses of nabiximols as adjunctive therapy compared with placebo on a clinical measure of velocity-dependent muscle tone in LLMT-6 in patients with MS who have not achieved adequate relief from spasticity with other antispasticity medications 	
 Change in LLMT-6; defined as the average of the 6 individual MAS transformed scores of knee flexors, knee extensors, and plantar flexors on both sides of the body, from Day 1 pre-dose to D21 and from Day 31 pre-dose to Day 51
Secondary Objectives	Secondary Endpoints

 To evaluate the effect of multiple doses of nabiximols as adjunctive therapy compared with placebo on a clinical measure of velocity-dependent muscle tone in the lower limbs in LLMT-4 in patients with multiple sclerosis (MS) who have not achieved adequate relief from spasticity with other antispasticity medications To evaluate the safety and tolerability of nabiximols after administration of multiple doses 	
 Change in LLMT-4; defined as the average of the 4 individual MAS transformed scores of knee flexors and knee extensors on both sides of the body, from Day 1 pre-dose to D21 and from Day 31 pre-dose to Day 51 Frequency of treatment-emergent adverse events (TEAEs) Change from baseline to each assessment timepoint by treatment period for the following: 
 Clinical laboratory parameters Vital signs Physical examination procedure 12-Lead electrocardiograms (ECGs) Columbia-Suicide Severity Rating Scale (C-SSRS) at screening, and at each subsequent timepoint with reference to the last assessment (since last visit)

 To evaluate the PK profile of nabiximols after administration of multiple doses 	
 Plasma concentrations for Δ^9-tetrahydrocannabinol (THC) and its relevant metabolites (11-hydroxy-Δ^9-tetrahydrocannabinol and 11-carboxy-Δ^9-tetrahydrocannabinol) and cannabidiol (CBD) and its relevant metabolites (7-hydroxy-cannabidiol and 7-carboxy-cannabidiol) at distinct time points during each treatment period (Visits 2, 4, 5, 6, 8, and 9)
Exploratory Objectives	Exploratory Endpoints

 To evaluate the effect of multiple doses of nabiximols as adjunctive therapy compared with placebo on a clinical measure of velocity-dependent muscle tone in the lower limbs in LLMT-10 in patients with multiple sclerosis (MS) who have not achieved adequate relief from spasticity with other antispasticity medications To evaluate the effect of nabiximols after administration of multiple doses on walking using the T25FW test To evaluate the effect of nabiximols after administration of multiple doses on the following patient-reported outcomes: 
 The 11-point Numerical Rating Scale (NRS) spasticity score Daily spasm count The MS Spasticity Scale (MSS-88) total and subdomain scores 	
 Difference between treatment arm in change in LLMT-10; defined as the average of the 10 individual MAS transformed scores of knee flexors, knee extensors; plantar flexors, hip flexors and hip adductors on both sides of the body, from Day 1 pre-dose to D21 and from Day 31 pre-dose to Day 51 Difference between treatments in the change in T25FW test from Day 1 pre-dose to D21 and from Day 31 pre-dose to Day 51 Difference between treatments in average 11-point NRS spasticity score over the last 7 days of each double-blind treatment period Difference between treatments in average daily spasm count over the last 7 days of each double-blind treatment period Difference between treatments in total and subdomain scores of the MSSS-88 at the end of maintenance-dose phase of each double-blind treatment period

Table 9.1-2 Estimands

Estimands
Primary Estimand

The primary estimand for this study is defined by the following 4 components:
 
 • Population: Patients with MS, naïve to treatment with nabiximols who have not achieved adequate relief from spasticity with other antispasticity agents but have optimized treatment with at least 1 oral antispasticity drug. • Treatment: • Endpoint: Change in LLMT-6 from Day 1 pre-dose to D21 and from Day 31 pre-dose to Day 51. • Intercurrent events: 
 ○ Treatment-policy: Intercurrent events of non-adherence with IMP, use of prohibited medications, or other protocol deviations will be handled following a 'treatment-policy' strategy. Study data will continue to be collected and analyzed following the occurrence of the intercurrent event, i.e., the measure of effect is regardless of non-compliance, use of prohibited medications, or other protocol deviations. For patients who discontinue IMP, only the period in which this intercurrent event occurs will follow a treatment-policy strategy. Data will continue to be collected and analyzed following the occurrence of the intercurrent event up to the end of the period. ○ Hypothetical strategy: For patients who discontinue IMP during Period 1, their Period 2 data will be assumed to follow a hypothetical strategy, i.e., patients will be assumed to follow a similar pattern of data in Period 2 to those patients in the same Period 2 treatment arm who did not experience this intercurrent event during Period 1. For these patients, Period 2 data will not be collected, and these data will be imputed according to Table 9.1-3. 
Summary Measure: Mean difference in 'change from period level baseline to 21 days of the period assigned to nabiximols' compared to 'change from period level baseline to 21 days of the period assigned to placebo' regardless of treatment compliance and change of other antispasticity medications; following a treatment policy and hypothetical strategy for handling intercurrent events (as described above).

Secondary Estimand

The secondary estimand for this study is defined by the following 4 components:
 
 • Population: Patients with MS, naïve to treatment with nabiximols who have not achieved adequate relief from spasticity with other antispasticity agents but have optimized treatment with at least 1 oral antispasticity drug. • Treatment: • Endpoint: Change in LLMT-4 from Day 1 pre-dose to D21 and from Day 31 pre-dose to Day 51. • Intercurrent events: 
 ○ Treatment-policy: Intercurrent events of non-adherence with IMP, use of prohibited medications, or other protocol deviations will be handled following a 'treatment-policy' strategy. Study data will continue to be collected and analyzed following the occurrence of the intercurrent event, i.e., the measure of effect is regardless of non-compliance, use of prohibited medications, or other protocol deviations. For patients who discontinue IMP, only the period in which this intercurrent event occurs will follow a treatment-policy strategy. Data will continue to be collected and analyzed following the occurrence of the intercurrent event up to the end of the period. ○ Hypothetical strategy: For patients who discontinue IMP during Period 1, their Period 2 data will be assumed to follow a hypothetical strategy, i.e., patients will be assumed to follow a similar pattern of data in Period 2 to those patients in the same Period 2 treatment arm who did not experience this intercurrent event during Period 1. For these patients, Period 2 data will not be collected, and these data will be imputed according to Table 9.1-4. 
Summary Measure: Mean difference in 'change from period level baseline to 21 days during period assigned to nabiximols' compared to 'change from period level baseline to 21 days during period assigned to placebo' regardless of treatment compliance and change of other antispasticity medications; following a treatment policy and hypothetical strategy for handling intercurrent events (as described above).

9.2 Predetermined Covariates and Prognostic Factors and other Analyzed Factors

The following factors will be adjusted for as covariates and used in the analysis models as fixed effect:

- Treatment sequence, which has two levels: nabiximols/placebo (coded as 1) and placebo/nabiximols (coded as 2),
- Treatment period, which has two levels: Period 1 (coded as 1) and Period 2 (coded as 2),
- Baseline / Period baseline (as continuous covariates)

9.3 Analysis Sets

9.3.1 Treatment Arm

The “**as randomized**” **treatment arm** called the “planned treatment arm” is defined as the treatment allocated at each treatment period according to the randomization scheme.

The “**as treated**” **treatment arm also** called “actual treatment arm” is defined as the treatment received for the longest period of time within each treatment period.

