9.2.13 Interactive Response Technology

The IRT will be used to assign patients to treatment sequences, manage IMP supply, and to provide treatment allocation information in the event of patient unblinding.

A member of the trial team must contact the IRT at each clinic visit in order to perform the following:

- Randomize a patient (Visit 2)
- Obtain IMP dispensing information (Visits 2, 4, 6, and 8)
- Provide completion/early withdrawal information (Visit 9)

Training will be given to all sites prior to the start of the trial.

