9.3.2.4 Safety Analysis Set

All patients from the Screening Analysis Set, who received at least 1 dose of IMP in the trial will be included in the Safety Analysis Set and analysed according to the treatment received. Only patients for whom it has been confirmed that they did not take IMP will be excluded from the Safety Analysis Set. The Safety Analysis Set will be used to report all safety data using the actual treatment arm.

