12.4 Important Protocol Deviations

All important protocol deviations (IPDs) are defined in a study specific protocol deviation guidance and classified as presented in [Appendix 1](#). The IPDs that are determined to affect the primary efficacy results

will be classified as major IPDs as reported in Appendix 1 [Error! Reference source not found.](#). The occurrence of major IPDs will identify which patients maybe excluded from PP Analysis Set.

IPDs linked to COVID-19 will be identified. Patients for which at least one IPD has been identified, will be listed along with their deviation reason; demographics and treatment sequence for inclusion in the clinical study report (CSR) based on the deviation data will be entered into the clinical trial management system (CTMS).

The study team and the Sponsor will conduct ongoing reviews of the deviation data from both an internal system of record named Predictive Study Operations (PSO) and any other additional major IPDs that were missed and now identified through SAS programming of the blinded ADaM datasets, and the resulting set of evaluable patients throughout the study, adjusting the deviation criteria as seems appropriate. The PP Analysis Set must be finalized at the post-freeze data review meeting (or earlier), prior to database lock and unblinding. However, in case a patient is receiving a treatment kit he/she is not allocated to, this will be considered as a major IPD before unblinding but the impact on the PP Analysis Set will only be determined following unblinding. This particular case will clearly be identified prior to database lock.

Based on the Randomized Analysis Set, the number and percentage of patients with important protocol deviations by category, as well as the number and percentage of patient with IPDs linked to COVID-19, by category, will be summarized by treatment sequence and overall.

Based on the FAS, the number and percentage of patients with at least one major IPD and the number and percentage of patients with major IPDs linked to COVID-19 will also be summarized by treatment sequence and overall.

Using the Randomized Analysis Set and the Safety Analysis Set (if deemed necessary to account for any patients exposed out of randomization) IPDs will be listed by treatment sequence and patient identifier and flagged for belonging to FAS and Safety Analysis Set. In this listing major IPDs, and IPDs linked to COVID-19 will be identified.

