12.7.1 Adverse Events

Adverse events (AEs) will be coded using MedDRA 24.0 or higher according to the version in use at time of database lock. All safety analyses of AEs will be performed by actual treatment arm and reported using the Safety Analysis Set. An AE will be considered a TEAE if it first occurs or worsens in severity or seriousness after the first dose of IMP intake and before the last dose date + 15 days.

All AEs will be classified during the pre-treatment period, the 51-day safety on-treatment period or during the follow-up period as follows:

- Events that occurred before first IMP intake without worsening or becoming serious after the first IMP dose are classified as **pre-treatment AEs**;
- Events that occurred or worsens between first IMP dose and 14 days after IMP last dose are classified as on-treatment AE and are defined as **treatment-emergent AEs** (TEAEs);
 - TEAE occurring during 21-day on-treatment safety Period 1 will be considered emergent to actual treatment received during Period 1 (as defined in [Section 10.1.1](#)).
 - TEAE occurring during 21-day on-treatment safety Period 2 will be considered emergent to actual treatment received during Period 2 (as defined in [Section 10.1.1](#)).
- Events occurring more than 15 days after last dose are classified as **follow-up AEs**.

Consequently, TEAEs will be summarized by treatment arm using the actual treatment received at each given period. Any adverse event occurring during the wash-out period will be linked to the actual treatment arm defined for Period 1, whereas any AEs occurring after last IMP dose will be linked to the actual arm defined at time of permanent study drug discontinuation.

The following events will not be identified as AEs in this study:

- Medical or surgical procedures (e.g., surgery, endoscopy, tooth extraction, etc.). The condition (the “triggering event”) that leads to the procedure are adverse events and will be reported as such.
- Pre-existing conditions present or detected prior to the first dose of study drug that do not worsen during the study.

Counting rules

For incidence reporting, if a patient reported more than one AE that was coded to the same preferred term/system organ class within a given treatment arm, the patient will be counted only once for that specific preferred term/system organ class by treatment arm and the rules defined below will be applied.

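### In a treatment period affected by a kit error, the longest-received rule for actual treatment tabulates safety data under a treatment the patient was not taking

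*SAP*

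**What the plan says.** SAP 9.3.1 separates the planned arm, which follows the randomisation, from the actual arm, which "is defined as the treatment received for the longest period of time within each treatment period". That produces a single label for each patient and period.

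SAP 9.3.2.4 says safety patients are "analysed according to the treatment received" and then: "The Safety Analysis Set will be used to report all safety data using the actual treatment arm". SAP 12.7.1 carries this through to adverse events: "TEAEs will be summarized by treatment arm using the actual treatment received at each given period". For Period 1 it says "TEAE occurring during 21-day on-treatment safety Period 1 will be considered emergent to actual treatment received during Period 1", with parallel wording for Period 2. For the gap between periods it says "Any adverse event occurring during the wash-out period will be linked to the actual treatment arm defined for Period 1". Events after the last dose go to the actual arm at permanent discontinuation. The at-risk denominator in 12.7.1 is built on the same 9.3.1 arm. The laboratory, ECG and vital-sign tables (12.7.3, 12.7.5.2, 12.7.4) are also by treatment arm.

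Protocol 5.3.4 has study drug dispensed at Visits 2, 4, 6 and 8, and returned at Visits 4, 5, 8 and 9. Each period therefore has two kits that follow one another.

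The SAP anticipates dispensing errors. Section 12.4 says that "in case a patient is receiving a treatment kit he/she is not allocated to, this will be considered as a major IPD", and Appendix 1 lists this as major deviation 16. Section 12.4 goes on to deal with the Per Protocol set. It does not say how safety data from such a period are attributed.

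**The concern.** The planned and actual arms differ only when a patient receives a treatment other than the allocated one. The actual-arm rule exists for that case, so it should give a sensible answer there.

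Because the first kit of each period covers far more days than the second, the label follows the first kit. If the two kits hold different treatments, whatever is recorded on the second is reported under the first. For example, a placebo-period patient handed nabiximols at Visit 4 would have later TEAEs, washout events and Visit 5 laboratory and ECG results tabulated as placebo. The reverse error, placebo handed out in a nabiximols period, adds placebo-time data to nabiximols.

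The data at risk are not marginal. The second kit covers the maintenance phase and the period's only scheduled on-treatment laboratory and ECG assessments. The safety subgroup by mean daily sprays (SAP Table 12.7-1) also uses maintenance-phase sprays. In a trial of this size, single serious or rare events are read individually.

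**Working it through.** **Inputs.** Dispensing at Visits 2/4 and 6/8 (Protocol 5.3.4). Visit 4 on Day 15 ± 1 and Visit 5 on Day 21 ± 2 (Protocol 9.1.2.3). Visit 6 on Day 31 ± 1 (9.1.4.1). Visit 8 on Day 45 ± 1 and Visit 9 on Day 51 ± 2 (9.1.4.3). Interruptions are ignored, as in the exposure rule of SAP 12.3.1.1; 9.3.1 does not say how duration is counted.

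**Formulas, Period 1.** First-kit days = Visit 4 day − 1. Second-kit days = Visit 5 day − Visit 4 day + 1.

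**Plan's own figure.** Nominal schedule: 15 − 1 = 14 and 21 − 15 + 1 = 7, total 21. This reproduces the stated 21 days of administration, split about 14 and 7.

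**All permitted Period 1 windows.**

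| Visit 4 day | First kit (days) | Second kit, Visit 5 on Day 19 / 21 / 23 (days) |
|---|---|---|
| 14 | 13 | 6 / 8 / 10 |
| 15 | 14 | 5 / 7 / 9 |
| 16 | 15 | 4 / 6 / 8 |

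The first kit covers 13-15 days and the second 4-10. The closest case is 13 against 10. Counting the Visit 4 day to the first kit only widens the gap.

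**Tightest Period 2 case.** Visit 6 on Day 32, Visit 8 on Day 44, Visit 9 on Day 53: Days 32-43 = 12, against Days 44-53 = 10. The second kit is still shorter.

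**Where this breaks.** Outside the windows the second kit can be longer: Visit 4 on Day 12 with Visit 5 on Day 23 gives 11 against 12. If only dosed days count, a pause during titration could also reverse the order: at least 14 − 7 + 1 = 8 days on the nominal schedule, or 13 − 10 + 1 = 4 days in the closest Period 1 case.

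**What is mislabelled after a wrong kit at Visit 4 or 8 only (nominal days).**
- Dosing days: 7 of 21 (33%).
- Adverse-event days carrying the Period 1 label: Days 15-30, 16 of 30 (53%), washout included.
- Adverse-event collection days in Period 2: Days 45-58, 14 of 28 (50%).
- Scheduled on-treatment laboratory tests and ECGs: all of them, since they occur only at Visits 5 and 9 (Protocol Appendix 1).
- Sprays, on the example titration schedule with 12 per day maintained: Days 1-14 total 102; Days 15-20 at 12 plus 6 on the morning of Day 21 = 78; 78/180 = 43%. If the Day 15 morning dose comes from the first kit, as the schedule suggests (no site dosing at Visit 4), it is 72/180 = 40%.

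**Wrong kit at Visit 2 or 6 only.** The label follows the wrong kit. Everything after the correct kit starts is mislabelled, again including all scheduled laboratory and ECG data.

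**Size per patient.** One misattributed patient with an event is 1/68 = 1.5 points, using the 68 completers in SAP 8.2. If the 10% dropout allowance were reapplied (an assumption; 68/0.9 rounds up to 76), it is 1/76 = 1.3 points.

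**The case against.** The strongest reply is that the issue is contingent and partly covered already. Kits are assigned centrally by the interactive response system. The documents give no mis-dispensing rate, and with no error the effect is nil. Randomised-arm efficacy is untouched. All of that stands, and it limits the size of the point.

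Several stronger readings are tempting and are not supported:

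- A reader might infer that a wrong kit would go unrecognised. It would not: it is major deviation 16, identified before database lock and listed by patient. Drug concentrations at Visits 5 and 9 are also listed individually (SAP 12.6). Only the arm label in the safety tables is insensitive.
- A reader might include C-SSRS. SAP 12.7.5.3 attributes it by first and last dates of intake of each treatment.
- A reader might say nabiximols exposure is certainly dropped. SAP 10.7 and 12.3.1.1 define exposure for each study drug but take dates from period-level forms. That is ambiguous, not a demonstrated omission.
- A reader might see a contradiction between 9.3.2.4 and 9.3.1. The first refers to the actual arm and the second defines it, so the definition is too coarse rather than inconsistent.
- A reader might conclude that nabiximols harms are understated. The error runs either way, and neither direction is shown to be likelier.

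These limits do not touch the TEAE, laboratory, ECG and vital-sign tables. A deviation listing lets a reader reconstruct the problem but does not correct the tables.

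**Conclusion.** The point holds in a bounded form. Inside the visit windows and ignoring interruptions, a wrong-treatment kit given only at Visit 4 or 8 cannot change the safety label, and one given only at Visit 2 or 6 fixes the wrong label on later data. In both cases the Visit 5 or 9 laboratory tests and ECGs are tabulated under a treatment the patient was not taking. After a wrong Visit 4 or 8 kit, so are about half of the period's adverse-event days.

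The number of patients affected cannot be computed from the documents and may be zero; per affected patient with an event the shift is about 1.3 to 1.5 points. The case for acting is that the rule gives a wrong answer in the one situation it is written for, which the SAP itself foresees, and that choosing an attribution after unblinding would be post hoc.

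**What to change.** In SAP 9.3.1 and 12.7, for any period in which both treatments were received:

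1. Attribute each TEAE and each safety assessment to the treatment of the kit in use at onset or assessment. Use the IRT kit log, reconciled with the site accountability record in Protocol 5.3.4. This matches the intake-date rule already used for C-SSRS.
2. Count the patient as at risk, with exposure days, under each treatment actually received, and align 10.7 and 12.3.1.1 with this.
3. State how events soon after a switch are attributed, and how censoring works for these patients in the Kaplan-Meier analyses of adverse events of special interest (12.7.2.3).

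Efficacy stays as randomised. Labelling the whole of any such period as nabiximols is not recommended: it would move placebo-time events to nabiximols and replace one misattribution with another.

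The cost is a short text change and minor extra programming, including the denominators and censoring. A kit-error patient will appear in both arms within one period, which needs a table footnote. Agree the rule before unblinding.
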